A growing number of clinical trials and demonstration projects have provided strong evidence for the efficacy of a once-daily oral pill (emtricitabine/tenofovir) as pre-exposure prophylaxis (PrEP) for the prevention of HIV among uninfected, at-risk individuals, including MSM [6–8] and injection drug users [9]. However, implementation of PrEP in at-risk populations such as MSWs has been limited by several concerns including adherence to the medication. In order to be most effective, PrEP adherence must be high (four or more doses per week) [10,11]. A body of evidence regarding adherence to PrEP is just beginning to emerge, suggesting that, similar to antiretroviral therapy (ART) among HIV-infected individuals, PrEP adherence may be suboptimal among individuals with psychosocial problems (e.g., substance use, depression, violence victimization). Given the complexity of sexual decision making for MSW, a PrEP uptake and adherence package would need to be responsive and tailored to MSWs’ distinct circumstances and contextual surroundings to optimize their likelihood of initiating PrEP, and sufficiently adhering to, this biomedical HIV prevention modality. Informed by our formative research (including individual qualitative interviews, focus groups, and a longitudinal epidemiological cohort study of HIV risk, in which all examined perceived PrEP acceptability) and programmatic work with US based MSWs over the past decade, we adapted the “Life-Steps” model [12,13]—a proven efficacious intervention for HIV treatment adherence among marginalized groups—for the provision of PrEP. The resulting theory-based intervention, PrEPare for Work—developed by our interdisciplinary investigator team—addresses access to and uptake of PrEP, and provides skills training to optimize adherence. As such, the PrEPare for Work intervention includes two components: 1) Strength-based case management for PrEP access and initiation, and 2) Cognitive-behavioral theory-based PrEP adherence counseling by a trained masters-level counselor—both as part of a comprehensive, context-specific approach to HIV prevention for MSW in Providence, Rhode Island. Providence, often described as the epicenter of male sex work, has one of the largest populations of street-based MSWs in the US [4].

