## RESEARCH PROTOCOL

**Specific Aim 1 - Pilot RCT:** To evaluate both PrEP initiation and adherence, we will use a two-stage randomization design. In Stage 1, we plan to enroll 130 MSW (65 per randomization arm to achieve N=104 completers for Stage 1; ~80% retention), who will be equally randomized to receive either the PrEPare for Work strength-based case management (SBCM) or standard of care (i.e., referrals only) to evaluate successful PrEP initiation. In Stage 2, those who initiate PrEP (n~44; ~80% in Stage 1 intervention arm and ~20% in Stage 1 comparison arm), regardless of their Stage 1 randomization condition, will then be equally randomized to the PrEPare for Work adherence intervention condition or standard of care comparison condition (22 per randomization arm to achieve N=40 completers for Stage 2; ~90% retention). While we are aware that there may be important differences that affect adherence in those who initiate PrEP without additional SBCM and those who received SBCM, we anticipate that randomization at the second stage will balance out potential confounding by level of motivation to initiate PrEP. See point of contact diagram below for specific details.

**Recruitment:** All participants will be identified by staff at Project Weber, our community partner organization and study site for this study, and will live in or participate in sex work in RI. In addition to identifying participants at the drop-in center, participants will be recruited from a variety of sources: (1) members of our recruitment/outreach team will actively recruit participants in the community via direct outreach at venues where we know sex workers solicit clients (such as bars, night/dance clubs, on the streets), (2) via the internet, by posting study related advertisements which may include a brief anonymous self-administered pre-eligibility assessment, (3) via direct engagement with internet escorts on the internet for which

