**Screening and Enrollment:** As part of the screening process, a brief anonymous pre-eligibility assessment may be conducted online or by phone prior to the full eligibility screening. The full eligibility screening may take place by phone, in a private room at one of the study sites (Brown University, Project Weber or The Miriam Hospital); or in a public location (coffee shop, library, etc) where the participant feels most comfortable. Participants will be asked to complete a survey assessing demographic information, sexual orientation, ethnic/racial identity, education level, history of HIV and other STDs, history of HIV testing, access to HIV and STD diagnostic and treatment services, recent sexual behavior, characteristics of recent partners, use of PEP previously and knowledge and anticipated acceptability of PrEP and other new biomedical prevention methods. The screening visit will take place in a private room at one of the study sites (Brown University, Project Weber or The Miriam Hospital); the participant can select where he feels most comfortable. Enrollment will be limited to participants who are English -speaking, HIV-uninfected, report having exchanged sex for money or drugs with another man in the past three months in RI, report at least one episode of condomless anal intercourse with an HIV-infected or unknown serostatus partner in the previous three months, who express an interest in using PrEP as an HIV prevention tool and live in the New England area. Potential participants will be asked to undergo antibody testing for HIV as well as screening for Hepatitis B infection (Hepatitis B surface antigen and antibody) and renal insufficiency (serum creatinine). Individuals will also be screened for acute HIV infection. A release of medical information will be requested upon enrollment. Only information regarding the PrEP clinic visit is requested and completion of the release is voluntary.

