Statistical Analysis Plan

September 15, 2015

Optimizing PrEP Uptake & Adherence Among Male Sex Workers (MSW)
Using a 2-stage Randomization Design
(NCT03086057)

Specific Aim 2: Pilot RCT. Initially, the distribution of all variables will be assessed, as will the autocorrelations across time between all study variables and the primary outcomes. Dependent variables will be examined to determine which distributional models are most appropriate for subsequent statistical procedures. We will examine the equivalence of the random assignment of groups with regards to key baseline characteristics, including socio-demographics and sexual risk-related variables. In the unlikely event that randomization does not work to balance these characteristics at baseline, we will assess whether baseline differences may account for differences in outcomes. Attrition effects will be evaluated by testing whether systematic differences exist between those participants who complete the research versus those who drop out. In this way, we can determine the nature of the potential bias introduced by attrition from the study.

Primary Analysis. The primary analysis for Stage 1 will compare PrEP initiation at 1-month post Stage 1 randomization between the study arms. For stage 2, the primary analysis will compare adherence (defined by percent of drug in blood) at the 3 and 6 month visits between the study arms. Changes in self-reported adherence, sexual behavior adjustment and substance use will also be examined. Moreover, group differences in number of PrEP clinic appointments kept will be compared. All analyses will use two-tailed tests of significance, with significance at alpha = 0.05. We will use generalized linear models (GLM) with properly-chosen link functions to analyze longitudinal data for each analysis. The GLMs will be estimated using generalized estimating equations with robust standard error estimates (GEE)^{67,68}, which provides an extension of regression analysis to the case of correlated or repeated observations and allows for inclusion of both categorical and count dependent variables and for appropriate modeling of covariance structures when observations are correlated across time. We will follow an intent-to-treat model, analyzing participants in the study arm to which they were assigned, regardless of fidelity to assigned group.

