Power and Sample Size Considerations. As a pilot study, the primary emphasis is on feasibility of the two arms and hence power is limited; and to find statistical significance, the effect sizes would need to be large. However, the number of repeated measures does increase power for the longitudinal analyses. For stage 1, proportion of participants in each condition who initiate PrEP, with a two-tailed p-value of 0.05, and 53 participants per arm, we would need at least a 30 percentage point difference across the two conditions (e.g., if 20% of the comparison arm and 50% of the intervention arm initiated PrEP) to achieve 80% power. For stage 2, percent adherence since the last visit will be assessed yielding 3 repeated blood-drug levels across baseline, 3, and 6. With a two-tailed p-value of 0.05, group sample sizes of 22 participants per arm, assuming a correlation of 0.80 between repeated adherence measures and with up to 10% attrition there will be greater than 80% power to detect in excess of a medium effect size difference (approximately 10% in the slope) between the intervention and comparison groups. For categorical outcomes (e.g. percent of patients in each condition achieving at least 90% adherence via blood drug levels), with a two-tailed p-value of 0.05, the three repeated measures, and 22 patients per arm, we would need at least a 25 percentage point difference across the two conditions (e.g., if 50% of the comparison arm and 75% of the intervention arm had at least 90% adherence) to achieve 80% power.

Missing Data. We will assess for patterns of missing data, which are expected to be low as the study utilizes A-CASI. We will explore strategies for imputing missing data based on patterns of missingness and apply appropriate techniques, applying sensitivity analysis to determine the optimal method of handling the missingness⁷¹⁻⁷³.

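### Baseline variables reach the arm comparison only through an undefined balance check, and the Stage 1 primary analysis names no covariate, which costs some precision and leaves the model open

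*SAP*

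**What the plan says.** The opening paragraph of the SAP (Specific Aim 2: Pilot RCT) states: "We will examine the equivalence of the random assignment of groups with regards to key baseline characteristics". It gives socio-demographics and sexual risk variables as examples. Its next step, which concerns outcome differences, reads: "In the unlikely event that randomization does not work to balance these characteristics at baseline, we will assess whether baseline differences may account for differences". No test, threshold or margin is attached to the check, and the SAP does not say whether a failed check would change the primary model.

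The SAP's Primary Analysis paragraph compares PrEP initiation at one month between the Stage 1 arms and names no covariate. It plans generalized linear models fitted by GEE, without a covariate list, and adds: "All analyses will use two-tailed tests of significance, with significance at alpha = 0.05".

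The Protocol (Research Assessments) schedules an ACASI survey at Stage 1 baseline. Its domains include alcohol and drug use, depression and anxiety, and attitudes to PrEP. The screening survey (Screening and Enrollment) also covers "knowledge and anticipated acceptability of PrEP and other new biomedical prevention methods". The Protocol's Background section links substance use and depression to poorer PrEP adherence.

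**The concern.** If allocation was properly random, any baseline difference is chance. A check on whether randomisation worked therefore does not help to decide whether to adjust. What matters is how strongly a variable predicts the outcome. A strong predictor is worth including when the arms look balanced, and a weak one is hardly worth including when they do not.

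Two things are at stake. The first is precision: a small trial that collects plausible predictors would use them only when an imbalance happens to be noticed. The second is discretion: with no criterion, no covariate list and no stated consequence, the analysis can be settled after the data are in hand.

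**Working it through.** **Inputs.** From the Protocol: Stage 1 "65 per randomization arm to achieve N=104 completers for Stage 1; ~80% retention", so 104/2 = 52 completers per arm; Stage 2 has 22 per arm. From the SAP: two-sided alpha 0.05; 53 per arm for Stage 1; 20% v 50%. Assumed, because the documents do not say: the form of the balance check, the number of variables checked, the covariate–outcome correlation, and the 20% v 45% scenario.

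**1. The SAP's own power figure.** The SAP says: "and 53 participants per arm, we would need at least a 30 percentage point difference across the two conditions", with 20% v 50% as the example for 80% power. Normal approximation, with p̄ = 0.35:

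- z = (0.30·√53 − 1.96·√(2·0.35·0.65)) / √(0.2·0.8 + 0.5·0.5) = (2.184 − 1.322)/0.640 = 1.346, so power is 91% (Fisher's exact test: 88%).
- 80% power for 20% v 50% needs 39 per arm (45 with continuity correction).
- At 53 per arm, 80% power corresponds to a difference of about 25 points; 20% v 45% gives 79%.

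The stated 80% is not reproduced, and the discrepancy is conservative. That is a separate matter. It is relevant here because adjustment has less to add at 20% v 50%. The 20% v 45% scenario below is used because unadjusted power there is close to 80%.

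**2. What a 5% baseline test would flag (assumption).** The smallest observed standardised difference reaching p < 0.05 is t(0.975; 2n−2)·√(2/n).

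- 65 per arm: 1.979 × 0.1754 = 0.35 SD.
- 22 per arm: 2.018 × 0.3015 = 0.61 SD.

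The share of chance imbalances larger than d that go unflagged is 1 − 0.05/[2(1 − Φ(d/√(2/n)))].

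| d | 65 per arm | 22 per arm |
|---|---|---|
| 0.2 SD | 80% | 90% |
| 0.3 SD | 43% | 84% |

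With 10 independent variables, the chance of at least one flag under perfect randomisation is 1 − 0.95^10 = 40%.

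**3. What adjustment would gain in Stage 1.** As an approximation, n per arm acts like n/(1 − R²). From 53 per arm and a 20% control rate:

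| Assumed R² | Acts like, per arm | Difference detectable at 80% power | Power, 20% v 45% |
|---|---|---|---|
| 0 | 53 | 25.2 points | 79% |
| 0.05 | 56 | 24.5 | 81% |
| 0.10 | 59 | 23.8 | 83% |
| 0.20 | 66 | 22.3 | 88% |
| 0.30 | 76 | 20.8 | 92% |

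Simulation with 52 per arm, 20% v 45%, one continuous covariate and 20,000 trials per setting. The adjusted analysis is a linear risk-difference model with robust standard errors. The gated rule adjusts only if the baseline test is significant.

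| Assumed correlation | Gated rule | Always adjust |
|---|---|---|
| 0.1–0.2 | about 79–80% | about 80% |
| 0.3 | 79% | 82% |
| 0.4 | 80% | 85% |
| 0.5 | 81% | 89% |

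Never adjusting also gives about 79–80%. With no treatment effect, always adjusting cut the variance of the estimated difference by about 7%, 14% and 24% at correlations of 0.3, 0.4 and 0.5; the gated rule cut it by about 2%, 4% and 7%. At 20% v 50%, always adjusting moves power from about 91% to 91–97% over the whole range.

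**4. Type I error.** With 35% in both arms and correlations of 0.3–0.5, overall rejection was 5.0–5.6% unadjusted, 5.1–5.7% always adjusted and 4.4–5.1% under the gated rule.

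**The case against.** The strongest reply is that an unadjusted randomised comparison is valid, so prespecified adjustment is a matter of efficiency in a pilot whose stated emphasis is feasibility. That stands, and it limits how much weight the point can carry.

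The gain may also be small. It is close to zero for weak predictors. If the Protocol's expected initiation of about 80% v 20% is right, power exceeds 99.9% without adjustment. The same holds if those percentages are read as shares of the 44 initiators: 35/52 = 67% v 9/52 = 17%. PrEP attitudes may predict less than hoped, because eligibility already requires willingness to start PrEP.

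The SAP's step is not purely about imbalance: once triggered, it asks whether the variable relates to outcome. Its list of characteristics is illustrative. Nor are baseline data otherwise unused. The attrition comparison and moderator interactions do not depend on the check, and the baseline drug level is counted among the Stage 2 repeated measures in the power section. None of this puts a covariate into the Stage 1 primary model.

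Three stronger readings are tempting, and the documents do not support them:

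- **That the SAP takes a non-significant baseline comparison as proof of equivalence.** It names no baseline test and never says this. The 0.05 level is stated in the Primary Analysis paragraph, so applying it to the baseline check is an inference.
- **That important imbalances are mostly missed.** This depends on size and stage, as step 2 shows. Power calculations against a true baseline difference are beside the point, because randomisation makes the true difference zero.
- **That the error rate exceeds 5%.** This holds only within a selected slice. In the roughly 14% of trials with a baseline |z| of 1.3–1.96, the unadjusted test rejects a true null in 7–9% of cases, against 5–6% adjusted. Over all trials there is no inflation.

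**Conclusion.** The point holds as a cheap improvement, not as a flaw that invalidates the analysis. Observed imbalance, judged by no stated rule, is the only stated trigger for considering baseline variables in the arm comparison, and the Stage 1 primary names no covariate. The cost is lost precision and an analysis left to discretion; there is no average bias and no overall type I inflation.

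At 52 per arm and an assumed 20% v 45%, always adjusting is worth anything from almost nothing to about 8–9 points of power over assumed correlations of 0.1 to 0.5. At the SAP's own 20% v 50% it is worth at most about 6 points. The gated rule recovers little of this. If the SAP's assessment would never alter the primary model, the loss is about the same, since never adjusting gives nearly the same power. The flagging thresholds and the 40% figure rest on a 5% baseline test, and the latter also on 10 independent variables.

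**What to change.** - Report baseline characteristics by arm descriptively, without a judgement of equivalence, and delete the sentence that makes failed balance the trigger.
- Before outcomes are examined by arm, name one or two prognostic baseline covariates for the Stage 1 initiation model, to be included whatever the balance. Recent substance use and a PrEP attitudes measure are candidates already in the survey.
- Report a standardised risk difference with a 95% confidence interval, with the unadjusted comparison as a sensitivity analysis.
- Optionally, fix one baseline predictor for Stage 2 in the same way.

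The cost is a few lines of SAP text and one or two model terms, with no new data or participants. The downside is that the covariates must be chosen in advance, and the gain is near zero if they predict weakly.

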**Inclusion criteria:**

- 18 years of age or older
- Assigned male at birth
- Report having exchanged sex with another man for money or drugs in the past three months
- Report behavioral risk for HIV infection, consistent with Centers for Disease Control and Prevention guidelines for prescribing PrEP: condomless anal intercourse with at least one HIV-infected or unknown serostatus partner in the past three months
- HIV-negative by antibody test \*Stage 2
- Able to understand and speak English, for consenting and counseling
- Lives in the New England area
- Willing to initiate PrEP

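### The outcomes examined as changes have no stated arm contrast and no baseline covariate; adjusting for baseline would be a free gain in precision

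*SAP*

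**What the plan says.** The Primary Analysis paragraph of the SAP sets both primary analyses as comparisons between arms: PrEP initiation at one month in Stage 1, and drug level in blood at 3 and 6 months in Stage 2. It then adds: "Changes in self-reported adherence, sexual behavior adjustment and substance use will also be examined". That sentence gives no contrast, visit or baseline term. The next sentence does name a contrast, for a different outcome: "group differences in number of PrEP clinic appointments kept will be compared".

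The rest of the paragraph applies to all of these. On the model: "We will use generalized linear models (GLM) with properly-chosen link functions to analyze longitudinal data for each analysis", estimated by GEE, with two-sided tests at 0.05. On the assignment rule: "analyzing participants in the study arm to which they were assigned, regardless of fidelity to assigned group". The SAP's opening paragraph checks balance on baseline characteristics, including sexual-risk variables, and takes baseline differences further only if the arms turn out unbalanced.

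In the Protocol, the Inclusion criteria require every man to report "condomless anal intercourse with at least one HIV-infected or unknown serostatus partner in the past three months"; Screening and Enrollment repeats this. No level of substance use is required. In the behavioural criteria, drugs appear only as a form of payment: "Report having exchanged sex with another man for money or drugs in the past three months". Under Research Assessments, ACASI surveys covering sexual behaviour and alcohol and drug use are taken at the baseline of each stage, at 1 and 2 months in Stage 1, and at 3 and 6 months in Stage 2.

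**The concern.** There are two separate issues.

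The first is precision, and it covers both sexual behaviour and substance use. If the analysis follows the wording and compares changes from baseline, it subtracts the whole baseline value whatever its correlation with follow-up. Regressing on baseline removes only the part that predicts follow-up, and so gives a smaller variance for the same randomised contrast. The trial is small: Stage 1 plans "65 per randomization arm to achieve N=104 completers for Stage 1; ~80% retention" and Stage 2 plans "22 per randomization arm to achieve N=40 completers for Stage 2; ~90% retention". The baseline values are already being collected.

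The second is interpretation, and it covers sexual risk only. Men enter because they recently had a qualifying act, so the Stage 1 baseline is selected high. With stable behaviour, some men will report no such act in a later period. Because the sentence speaks only of changes, a reader of the results could take a fall within one arm, or within the whole sample, as evidence that the intervention reduced risk or that PrEP did not raise it.

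**Working it through.** The documents give no power, SD, effect size or correlation for these outcomes, so there is no planned figure to reproduce. The SAP's correlation of 0.80 is stated for repeated adherence measures only. I therefore assume r from 0.3 to 0.8. The numbers analysed are the Protocol's completers: 104/2 = 52 per arm in Stage 1 and 40/2 = 20 per arm in Stage 2.

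**1. Precision of the between-arm contrast.** For a continuous outcome with unit variance at each visit and no selection, the per-person variance with one follow-up is 2(1−r) for the change score and 1−r² with baseline as covariate. The ratio is (1−r²)/[2(1−r)] = (1+r)/2. For the mean of two follow-ups with equal correlations, the variances are (1+r)/2 + 1 − 2r and (1+r)/2 − r².

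| r | One follow-up: change | Adjusted | Ratio | Two follow-ups: change | Adjusted | Ratio |
|---|---|---|---|---|---|---|
| 0.3 | 1.40 | 0.91 | 0.65 | 1.05 | 0.56 | 0.53 |
| 0.5 | 1.00 | 0.75 | 0.75 | 0.75 | 0.50 | 0.67 |
| 0.8 | 0.40 | 0.36 | 0.90 | 0.30 | 0.26 | 0.87 |

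Below r = 0.5 the change score has variance above 1, so it is less precise than ignoring baseline altogether. With 20 per arm, one follow-up, a 0.5 SD difference and r = 0.8, power is 75% adjusted and 71% on change: 0.5/√(2×0.36/20) − 1.96 = 0.68, and 0.5/√(2×0.40/20) − 1.96 = 0.54.

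**2. The gain shrinks if baseline is selected.** As an illustration, restrict entry to the upper half of a normal risk score. The baseline variance becomes 1 − 2/π = 0.363, the change-score variance is (1−r)²×0.363 + 1 − r², and the adjusted variance stays at 1 − r². The ratios are 0.91/1.088 = 0.84, 0.75/0.841 = 0.89 and 0.36/0.375 = 0.96 at r = 0.3, 0.5 and 0.8. At the limit, if the outcome is the same yes/no item used for entry, every man is positive at Stage 1 baseline. Change is then follow-up minus a constant, the ratio is exactly 1, and there is no covariate to use.

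**3. Within-arm fall with no effect.** Under the same upper-half restriction, the expected change is −(1−r)×√(2/π) = −(1−r)×0.798, which is −0.56, −0.40 and −0.16 SD at r = 0.3, 0.5 and 0.8. In 4,000 simulated trials per setting with no intervention effect, a within-arm test was significant in 63%, 45% and 20% of trials with 20 per arm, and in 97%, 87% and 47% with 52 per arm. The between-arm difference averaged about zero throughout (20, 22 or 52 per arm). It was significant in 4.6% to 5.5% of trials on change scores and in 4.5% to 5.9% with baseline adjustment.

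**4. Size of the fall on the trial's own scale.** For a yes/no item with stable prevalence p and between-period correlation φ, P(yes later | yes at entry) = p + φ(1−p). With φ from 0.3 to 0.7 this is 0.48 to 0.78 at p = 0.26 and 0.72 to 0.88 at p = 0.60, a fall of 12 to 52 points. For gamma-Poisson counts with mean m and shape k, selected at one or more, the proportional fall is (k/(k+m))^(k+1). It is 35% at k = 0.5, m = 0.5; 9% at k = 0.5, m = 2; 51% at k = 2, m = 0.5; and 3.5% at k = 0.1, m = 2. The documents supply none of these inputs. The 26% in the Protocol's Study Sites section concerns unprotected anal or vaginal sex with clients, not the entry criterion. The direction can be expected; the size cannot be derived.

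**The case against.** The strongest reply is that the plan does compare arms. The paragraph applies the GEE model to each analysis and keeps men in their assigned arm, and the Power section describes the adherence effect as a slope difference between groups. That stands: nothing commits the trial to reading a within-arm fall as an effect.

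A reader might go further and infer that selection at entry biases the trial's comparison and that baseline adjustment is the cure. The documents do not support this. Regression to the mean acts equally on both randomised arms and cancels in the contrast with or without adjustment, as step 3 shows. Adjustment buys precision, not validity.

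Nor can the selection argument be extended to substance use, because no level of use is required for entry. It also weakens for Stage 2: behaviour is measured again at that stage's baseline, so part of any fall in sexual risk may already have happened.

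It is also fair to say that (1+r)/2 is a textbook case, whereas the SAP plans repeated-measures GEE with links suited to categorical and count outcomes. The exact gain under that model is not shown here, and step 2 shows that it can be small. What survives is that the sentence names no contrast and no baseline covariate is prespecified.

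**Conclusion.** The point holds as a free improvement and is minor, because these are additional outcomes in a pilot that the SAP itself describes as mainly about feasibility. A between-arm comparison of changes would be valid but would usually give up precision. The variance saved by adjustment is 35%, 25% or 10% at r = 0.3, 0.5 or 0.8, assuming a continuous, unselected outcome with equal variances and one follow-up. It is 16%, 11% or 4% under the illustrative upper-half selection, and nil for a baseline that is constant by entry. For sexual risk alone, some fall from Stage 1 baseline is expected without any intervention effect. Its size is unknown, and a within-arm fall should not be reported as an effect.

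**What to change.** For sexual behaviour and substance use, replace the sentence with a statement along these lines: the arms will be compared at each named follow-up visit (1 and 2 months for the Stage 1 arms; 3 and 6 months for the Stage 2 arms) in the GEE model, with the pre-randomisation value of the same measure as a covariate where that value varies. The covariate is the Stage 1 baseline value for the Stage 1 arms and the Stage 2 baseline value for the Stage 2 arms. For sexual risk in Stage 1, use a count rather than the yes/no entry item. Add that change from baseline within an arm is descriptive only.

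The cost is SAP wording and one covariate per model, already collected by ACASI. No new data, visits or participants are needed.

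### Stage 2 GEE robust standard errors have no small-sample correction at 20-22 per arm; in the ordinary form, a single unadjusted contrast on the continuous outcome tests at about 6.2-6.4%, less under strong skew

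*SAP*

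**What the plan says.** The SAP's Primary Analysis paragraph sets the Stage 2 primary analysis to "compare adherence (defined by percent of drug in blood) at the 3 and 6 month visits" between arms. It adds that "All analyses will use two-tailed tests of significance, with significance at alpha = 0.05" and that "The GLMs will be estimated using generalized estimating equations with robust standard error estimates".

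The Power and Sample Size Considerations give "group sample sizes of 22 participants per arm", a correlation of 0.80 between repeated measures, up to 10% attrition, and "3 repeated blood-drug levels across baseline, 3, and 6". The detectable effect is described as "approximately 10% in the slope", which is a one-degree-of-freedom contrast. The protocol (Research Protocol, Specific Aim 1) agrees on 22 per arm and expects 40 completers, that is 20 per arm.

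Two statements limit the point. On the outcome distribution, the SAP's opening paragraph says: "Dependent variables will be examined to determine which distributional models are most appropriate for subsequent statistical procedures". On the purpose of the study, the power section says: "As a pilot study, the primary emphasis is on feasibility of the two arms and hence power is limited".

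Neither document names a finite-sample sandwich correction, a t or F reference, or a permutation alternative.

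**The concern.** The robust (sandwich) variance is justified by a large number of independent participants. With 20-22 per arm its ordinary form is biased downward, because it averages squared residuals without allowing for the estimated arm means. A normal reference then ignores the remaining uncertainty in that variance. Both faults act in the same direction, so tests reject too often and intervals are too short.

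In a pilot, the estimate and its interval are a main product, and here the interval would look slightly more precise than it is. The Stage 2 significance result also has a planned use: under Mediation analysis, the SAP explores mediators only if the adherence effect is significant. Finally, two analysts following the same sentence could choose different variance forms and report different p-values from the same data.

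**Working it through.** **Inputs.** 22 per arm randomised, 20 per arm completing, correlation 0.80, two-sided alpha 0.05 (SAP Primary Analysis and power section; protocol Specific Aim 1). The documents give no SD and no outcome distribution, so shapes are assumed and varied below.

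**The plan's own figure.** The SAP claims more than 80% power for an effect larger than medium. In outcome-SD units, the change from baseline to 6 months has SD sqrt(2 × (1 − 0.8)) = 0.632. The effect with 80% power is (1.96 + 0.842) × 0.632 × sqrt(2/n), which is 0.53 at n = 22 and 0.56 at n = 20. Taking 0.5 as medium, the claim is reproduced. The 10% slope figure cannot be checked without an SD.

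**Size of the ordinary test.** Take an unadjusted contrast of per-person means or slopes, with complete visits and an identity link. The uncorrected sandwich variance is (n − 1)/n of the unbiased one; a fitted GEE gave the same standard error as this formula (0.29703 both ways). Under normality:

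- Size = P(|t(2n−2)| > 1.96 × sqrt((n − 1)/n)).
- n = 20: cutoff 1.96 × 0.9747 = 1.910 on 38 df, size **6.37%**, coverage 93.6%.
- n = 22: cutoff 1.96 × 0.9770 = 1.915 on 42 df, size **6.23%**, coverage 93.8%.
- Interval width relative to exact: 1.910/2.024 = 0.944 and 1.915/2.018 = 0.949, so 5.6% and 5.1% too narrow.

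**Candidate corrections, same formula.** For this contrast Kauermann-Carroll restores the unbiased variance, and Mancl-DeRouen multiplies the unbiased variance by n/(n − 1).

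| Variance and reference | 20 per arm | 22 per arm |
|---|---|---|
| Uncorrected, normal | 6.37% | 6.23% |
| Uncorrected, t | 5.58% | 5.53% |
| Kauermann-Carroll, normal | 5.74% | 5.67% |
| Kauermann-Carroll, t(2n−2) | 5.00% | 5.00% |
| Mancl-DeRouen, normal | 5.15% | 5.13% |
| Mancl-DeRouen, t(2n−2) | 4.46% | 4.51% |

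**Other outcome shapes.** Simulated mean of the 3- and 6-month visits, correlation 0.8 before transformation, 200,000-400,000 null trials per setting (simulation SE 0.03-0.06 points). Each cell gives 20 / 22 per arm.

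| Shape | Uncorrected, normal | Kauermann-Carroll, t |
|---|---|---|
| Ceiling, first form | 6.33 / 6.27% | 5.00 / 5.03% |
| Ceiling, second form | 6.38 / 6.18% | 4.96 / 4.94% |
| U-shaped | 6.45 / 6.30% | 5.09 / 5.06% |
| Beta(4,1) | 6.33 / 6.20% | 4.94 / 4.97% |
| Log-normal, sigma 0.5 | 6.14 / 6.00% | 4.79 / 4.73% |
| Log-normal, sigma 0.8 | 5.77 / 5.69% | 4.35 / 4.42% |
| Log-normal, sigma 1.0 | 5.34 / 5.29% | 3.98 / 4.03% |

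**Slope contrast.** Arm, time and arm-by-time over 0, 3 and 6 months, exchangeable GEE, 20,000 null trials (SE 0.17 points), with 0% or 10% missing at month 6. Normal or ceiling data gave 6.1-6.6% uncorrected and 4.8-5.2% with Kauermann-Carroll and t(2n−4). Log-normal sigma 1.0 at 20 per arm gave 5.23% and 5.42% uncorrected, against 3.94% and 4.06% corrected.

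**The case against.** The strongest reply is that the SAP does not specify a wrong variance. It says robust and stops there; a corrected form would be consistent with its text. A reader might infer that the plan commits to an inflated test, and the documents do not support that. The figures describe what follows if the ordinary form is used. This part of the objection stands, and it makes the point one of an open choice whose ordinary reading is slightly anticonservative.

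Second, the consequence is small. An excess of 1.2-1.4 percentage points in a 44-person pilot will rarely change a decision. That also stands, and it sets the priority.

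Third, correction is not always an improvement. At log-normal sigma 1.0 the uncorrected test misses 5% by about 0.3 points and the corrected one by about 1.0 point on the conservative side. At sigma 0.8 the two misses are similar. The SAP leaves the distribution open, so the gain is clear only for roughly normal, bounded or mildly skewed outcomes.

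Fourth, the size depends on a contrast the SAP does not pin down. A reader might infer larger inflation: 7.56% and 7.30% (20 and 22 per arm) for a joint two-visit test on 2 df, or about 6.8-6.9% with a baseline covariate. The SAP states neither model for this comparison, so neither figure is claimed here. Which contrast is primary is a separate matter that this correction does not settle.

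**Conclusion.** The point holds at low priority. Without a named correction, the ordinary form of the stated method tests a single unadjusted Stage 2 contrast at about 6.2-6.4% under normal or bounded shapes instead of 5%, with 95% intervals about 5-6% too narrow. Under strong log-normal skew (sigma 1.0) the error is about 5.2-5.4%.

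This rests on four assumptions: an uncorrected sandwich, a normal reference, an identity link, and 20-22 participants per arm. The figures are exact only under normality with complete visits; the rest are simulated.

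A reader might extend the finding to the responder outcome of at least 90% adherence. That is not supported: simulated logit GEE for a binary outcome ran at about 4.7-5.2%. Nor does it reach the mediation and moderator results, which the SAP says it will not judge by significance.

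**What to change.** Add one sentence to the SAP's Primary Analysis naming a single estimator-reference pair for the Stage 2 continuous outcome:

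- Kauermann-Carroll variance with a t reference on participants minus parameters; or
- Mancl-DeRouen variance with a normal reference.

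The pair must be named together. A t reference alone leaves 5.5-5.6%, Kauermann-Carroll with a normal reference leaves about 5.7%, and Mancl-DeRouen with t over-corrects to about 4.5%. Check which the analysis software offers, since some GEE routines provide only Mancl-DeRouen. No existing SAP sentence is contradicted.

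**Cost.** With Kauermann-Carroll and t, intervals widen by 2.024/1.910 − 1 = 6.0% at 20 per arm and 2.018/1.915 − 1 = 5.4% at 22. By the noncentral t, a contrast with 80% power under the uncorrected test has 76.7% and 77.0%. The Mancl-DeRouen option costs nearly the same: its intervals widen by a factor n/(n − 1), that is 5.3% and 4.8%.

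If the outcome proves strongly skewed, the Kauermann-Carroll test will be conservative (about 4%) and further from 5% than the uncorrected one. Mancl-DeRouen was not simulated under skew. Its effective cutoff is close, however (1.96 × sqrt(20/19) = 2.011 against 2.024 at 20 per arm), so similar behaviour is to be expected. The SAP sentence should acknowledge this.
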